2.3.7.2 Other Safety Endpoints

- Vital signs:
 - Systolic Blood Pressure, Diastolic Blood Pressure, Heart Rate, Respiration Rate, Height, Weight, Temperature and presence of a clinically significant abnormal values.
- 12-Lead Electrocardiogram:
 - RR, PR, QRS, QT, HR, QTcB, QTcF, and the ECG interpretation. A central read cardiologist assessment of normal vs abnormal will be available as well as an investigator assessment of clinically significant vs not clinically significant.
- Physical examination abnormalities identified as preexisting before treatment will be recorded as medical history. Abnormalities identified after treatment will be recorded as adverse events.

- Laboratory samples will include:
 - Hematology, Chemistry, Immunochemistry and Urine Pregnancy.

2.3.8 *Pharmacokinetic Measurements*

There will be one PK sample at the Week 10 visit. The plasma concentrations of serlopitant and metabolites M1/M1a, M2/M2a and M3 will be determined.

2.4 **Study Day and Visit Windows**

Summary tables will report data based upon the protocol scheduled time points (Baseline, Weeks 2, 4, 6, 10 and Follow-up). Assessment will be assigned to these time points based upon the study day they are performed on. The derivation of study day depends upon whether the event occurred prior to or after treatment. This results in the first day of treatment being on day 1 and the day prior to the first day of treatment being day -1. For events that occur prior to the first day of treatment the following definition is used,

$$\text{Study day} = \text{date of assessment} - \text{date of first treatment}.$$

For events that occur on or after the first day of treatment, a plus one is added,

$$\text{Study day} = \text{date of assessment} - \text{date of first treatment} + 1.$$

The analysis windows used to report non-daily endpoints are outlined in [Table 3](#). If more than one assessment is available within the range, the assessment closest to the target day is reported for the analyses window. If two observations exist with the same distance to the target day, the first observation is used.

Table 3 Analysis Windows

Visit	Range	Target Day
Screening	< Day - 7	First
Baseline	Day -7 to Day 1	Day 1
Week 2	Day 2 to Day 21	Day 15
Week 4	Day 22 to Day 35	Day 29
Week 6	Day 36 to Day 57	Day 43
Week 10	> Day 57	Day 71

In addition to the analysis windows, data will be summarized at Follow-Up. The Follow-Up assessment will be the last assessment available that is at least seven days after the end of treatment. Should no post treatment assessments be available, the subject will not have a follow-up assessment. The baseline of an endpoint (see [Section 3.2](#)) may not always occur at the baseline visit.

The eDiary WI-NRS assessments will be summarized at Baseline, Week 2, 4, 6, 10, and Follow-up. The seven days leading up to the time point (see [Table 4](#) range), will be used to create the summary measures unless the subject does not have at least seven results. In this case, as many observations available within the complete data range will be used and additional data from the extended range (see [Table 4](#)) will be used until seven data points are achieved, or the end of the extended range is reached. An example of this algorithm can be found in [Section 3.4.1](#)

Table 4 Daily Windows

Visit	Range (complete data)	Extended Range
Baseline ^a	Day -7 to -1 or Day -6 to -1, Day 1	Day -11 to -8 or Day -10 to -7
Week 2	Day 8 to Day 14	Day 15 to Day 18
Week 4	Day 22 to Day 28	Day 29 to Day 32
Week 6	Day 36 to Day 42	Day 43 to Day 46
Week 8	Day 47 to Day 53	Day 54 to Day 57
Week 10	Day 64 to Day 70	Day 60 to Day 63

^a If the diary was completed prior to dosing on Day 1 then the baseline range includes the day of dosing (Day 1) otherwise the baseline range does not include Day 1.

An additional ‘Follow-Up’ timepoint will also be created. This timepoint includes the last 7 post treatment observations that are at least 7 days after the end of treatment.

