- Confirm next scheduled visit

6.5.10 *Week 10 Visit*

The Week 10 visit occurs 70 days (+ 3 days) after the Baseline visit. At the Week 10 visit, the following procedures and assessments are to be performed:

- Ask the subject to complete the WI-VAS, ESS, sPGA, and PGIC questionnaires
- Assess and record any changes in the subject's concomitant medications
- Female subjects should be queried for presence of new breast masses or abnormal discharge, and abnormal vaginal bleeding or discharge
- Assess and record any AEs and SAEs
- Obtain vital signs
- Perform a urine pregnancy test for females of childbearing potential and confirm the subject has a negative urine pregnancy test result prior to randomization (with positive or equivocal results confirmed by a serum pregnancy test)
- Draw blood for clinical laboratory tests (morning blood sampling due to Endocrine assessments)
 - Reproductive endocrine labs for females under 55 years of age at consent who are not using hormonal contraception or other hormonal therapies at Screening
 - Endocrine
 - Hematology
 - Chemistry
- Collect PK blood sample
- Perform targeted physical examination, including weight
- Review study drug compliance
- Collect returned study drug
- Review eDiary for compliance, re-train subject as needed
- Confirm next scheduled visit

6.5.11 *Follow-up Visit*

The required Follow-up visit occurs 35 days (+7 days) after the Week 10 visit or the last dose of study drug (for subjects who discontinue study drug early).

At the Follow-up visit, the following procedures and assessments are to be performed:

- Register visit into the IWRS

- Ask the subject to complete the WI-VAS, ESS, sPGA, and PGIC questionnaires
- Assess and record any changes in the subject's concomitant medications
- Female subjects should be queried for presence of new breast masses or abnormal discharge, and abnormal vaginal bleeding or discharge
- Obtain ECG
- Obtain vital signs
- Perform targeted physical examination, including weight
- Perform a urine pregnancy test for females of childbearing potential (with positive or equivocal results confirmed by a serum pregnancy test)
- Draw blood for clinical laboratory tests (morning blood sampling due to Endocrine assessments)
 - Reproductive endocrine labs for females under 55 years of age at consent who are not using hormonal contraception or other hormonal therapies at Screening
 - Endocrine
 - Hematology
 - Chemistry
- Assess and record any AEs and SAEs

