3.5.2 Clinical Laboratory Evaluations

Clinical laboratory results will be summarized by type of laboratory assessment (hematology, chemistry, endocrine), timepoint, and treatment. Summary statistics for actual values and changes from baseline will be tabulated by analysis window. Shifts from baseline clinical laboratory values based upon the normal range will be tabulated for each post baseline sample timepoint. These tables will utilize the normal ranges provided for the individual sample.

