3.5.4 Electrocardiogram Results

The overall ECG assessment (abnormal or normal) will be summarized by treatment and analysis window. The QTcF values will be summarized by treatment and analysis window as both the QTcF value and change from baseline. A summary of the number of subjects with a value > 450, 480 and 500, and the numbers of subjects with change from baseline values > 30 and 60 by treatment and analysis window will be produced.

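### The Week 10 window in SAP Table 3 has no end day, so off-drug Follow-up ECGs are tabulated as Week 10 and Follow-up WI-VAS and laboratory values can stand in for a missing Week 10 value

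*SAP*

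**What the plan says.** SAP 2.4 sets the reporting time points: "Summary tables will report data based upon the protocol scheduled time points (Baseline, Weeks 2, 4, 6, 10 and Follow-up"). It then gives the allocation rule: "Assessment will be assigned to these time points based upon the study day they are performed on". Nothing in the rule refers to the visit label or to whether the subject is still on treatment.

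Table 3 covers the non-daily endpoints. Weeks 2, 4 and 6 are closed ranges (Day 2-21, 22-35 and 36-57). Week 10 is everything after Day 57, with target Day 71. If several assessments fall in one window, the one closest to the target is used.

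Follow-Up is then added: "In addition to the analysis windows, data will be summarized at Follow-Up". Its definition is "The Follow-Up assessment will be the last assessment available that is at least seven days after the end of treatment". No sentence removes such an assessment from the Table 3 windows.

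The safety tables use these windows. SAP 3.5.4 says "The QTcF values will be summarized by treatment and analysis window as both the QTcF value and change from baseline", and counts QTcF threshold exceedances the same way. SAP 3.5.2 says of laboratory results: "Summary statistics for actual values and changes from baseline will be tabulated by analysis window".

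Protocol Table 2 and SAP Table 1 schedule ECGs at Screening, Week 4 and Follow-up, with none at Week 10. WI-VAS, the exploratory scales and laboratory samples are collected at both Week 10 and Follow-up.

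**The concern.** A Follow-up visit always falls after the end of treatment, and for a completer it always falls after Day 57. Under the written rule, its assessments qualify for Week 10 as well as for Follow-Up.

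This matters most for ECGs. Week 4 is the only scheduled on-drug ECG. A Week 10 row in the QTcF tables would read as a second on-treatment time point, while holding values taken five weeks or more after the last dose. A reader could take it as evidence about QTcF at the end of treatment, which the schedule does not collect.

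For WI-VAS, the exploratory scales and laboratory values, an attended Week 10 visit wins under the closest-to-target rule. The problem is limited to subjects with no Week 10 value but with a Follow-up value. Early stoppers are the main group, because Protocol 5.6 moves them into a follow-up period timed from the last dose. WI-VAS at Week 10 is a tested secondary endpoint, and SAP 2.7 limits imputation to WI-NRS. The open window would in effect fill some missing Week 10 WI-VAS values with much later ones, without saying so.

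**Working it through.** **Inputs**
- Study day on or after first dose = date - first treatment date + 1 (SAP 2.4).
- Protocol 6.5.10: "The Week 10 visit occurs 70 days (+ 3 days) after the Baseline visit".
- Protocol 6.5.11: "The required Follow-up visit occurs 35 days (+7 days) after the Week 10 visit or the last dose of study drug" (the latter for early stoppers).
- Plasma half-life of the parent drug: 45-86 hours (Protocol 1.3.1).
- Table 3 windows as above.

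**Reproducing the plan's own figures**
- Week 10 target: 70 + 1 = Day 71, as in Table 3.
- Lower cut: (43 + 71)/2 = 57, the midpoint between the Week 6 and Week 10 targets.

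**Completers**
- Week 10 visit: Day 71 to 71 + 3 = Day 74.
- Follow-up visit: 71 + 35 = Day 106 to 74 + 42 = Day 116.
- Distance from target: 106 - 71 = 35 days to 116 - 71 = 45 days. All of these days lie after Day 57, so all fall in Week 10.
- ECG: the Week 4 ECG falls on Day 26-32, inside the Week 4 window. The only later scheduled ECG is at Follow-up, so it becomes the Week 10 ECG and is reported again under Follow-Up.
- WI-VAS, scales and laboratory values: the Day 71-74 value is closer to target and is used if present. If it is missing, the Day 106-116 value is used.

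**Time off drug at Follow-up**
- 35 days = 840 hours.
- 840/86 = 9.77 half-lives and 840/45 = 18.67 half-lives.
- Fraction of parent drug remaining at the longer half-life: 2^-9.77 = 0.00115, or about 0.11%. This assumes simple exponential decay and does not count metabolites.

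**Early stoppers, last dose on Day d**

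Follow-up falls on Day d + 35 to d + 42.

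| Last dose | Condition | Table 3 window for Follow-up |
|---|---|---|
| Day 1-15 | d + 42 ≤ 57 | Week 6 |
| Day 16-22 | neither condition met | Week 6 or Week 10 |
| Day 23 or later | d + 35 ≥ 58 | Week 10 |

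The earliest possible Follow-up is 1 + 35 = Day 36, so the Week 4 window (ending Day 35) is never reached and the Week 4 ECG row is safe.

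**With Week 10 closed at Day 58-84** (Day 71 ± 13)
- Completers' Follow-up visits (Day 106-116) drop out.
- Early stoppers with 58 ≤ d + 35 ≤ 84, that is d = 23-49, still fall inside. At + 42 days the range is d = 16-42. Closing the window is therefore not enough for the safety tables; an off-drug rule is needed too.

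**Numbers affected**
- ECG: every completer with a Follow-up ECG, unless an unscheduled ECG after Day 57 is closer to Day 71.
- Other endpoints: the documents give no rate of missing Week 10 with attended Follow-up. As an assumption only, 2% × 200 = 4 and 10% × 200 = 20 subjects.

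**The case against.** The strongest reply is that SAP 2.4 names Follow-up as a time point of its own, so each assessment could be meant to go to one point only, with Follow-up visits going to Follow-Up. Follow-Up depends on end of treatment rather than study day, which would explain why it has no row in Table 3. In the same spirit, a programmer who consults SAP Table 1 might never produce a Week 10 ECG row. This reading is possible, but the SAP states no such precedence. The same list of time points includes Week 10, and the wording that introduces Follow-Up points to an additional summary rather than an exclusive one. The written rule gives the wrong label unless the programmer departs from it.

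Several limits do stand:
- The primary and weekly WI-NRS endpoints use the closed windows of Table 4.
- No scheduled on-drug ECG is displaced.
- Secondary p-values are descriptive (SAP 2.5).
- The half-life figure covers the parent drug only; Protocol 1.3.2 describes long-lived active metabolites and gives no half-life for them.
- For vital signs the link to Table 3 is less explicit: SAP 2.9 says by timepoint and SAP 3.5.3 by measurement day.

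It can also be said that the remedy still leaves some early stoppers' off-drug WI-VAS values in Week 10. That is deliberate: a value close to Day 71 belongs in an intent-to-treat comparison whether or not the subject is still on drug. A Day 106-116 value does not.

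**Conclusion.** The concern holds and should be fixed before unblinding. Followed literally, the SAP produces a Week 10 ECG and QTcF row made up of Follow-up ECGs, apart from any unscheduled ECG nearer Day 71. For completers these are 35-45 days past target and at least 35 days after the last dose, with about 0.11% or less of parent drug remaining under simple decay. The result is a mislabelled safety table that duplicates the Follow-Up row.

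For WI-VAS, the exploratory scales and laboratory values, the effect is confined to subjects with no Week 10 value and an attended Follow-up visit. Their number cannot be derived from the documents; 4-20 is an assumption. The primary analysis and the trial's decision rule are untouched.

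**What to change.** Amend SAP 2.4 and Table 3 as follows.

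1. Close the Week 10 window, for example at Day 58-84. The exact end day is a choice; any end day before Day 106 removes completers' Follow-up visits.
2. In the safety tables, assign every assessment made 7 or more days after the last dose to Follow-Up only, using the SAP's own 7-day threshold. This also clears early stoppers' Follow-up values from the Week 6 and Week 10 rows.
3. In SAP 3.5.4, present scheduled ECGs at baseline, Week 4 and Follow-up, with no Week 10 row.
4. For WI-VAS and the exploratory scales, apply the closed day window alone and state that off-drug values inside it are kept under the intent-to-treat approach.

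The cost is SAP wording and window code. A few more Week 10 WI-VAS values will be missing, and the SAP does not impute them. Because Follow-Up keeps only the last qualifying assessment, an occasional earlier off-drug laboratory value or unscheduled ECG would leave the by-window tables; it can be shown in a listing.

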8.9.2 Clinical Safety Laboratory Results

Clinical safety laboratory values will be measured by a central laboratory. Summary statistics for actual values and for changes from baseline will be tabulated for laboratory results by scheduled visit. Graphs of laboratory values over time will also be produced.

Subjects with clinical laboratory values outside of the normal reference range at any post-baseline assessment will be summarized. Shifts from baseline laboratory values will be tabulated.

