8.9.4 Electrocardiograms

The overall ECG assessment (abnormal or normal) will be summarized and descriptively characterized, along with a summary of how many subjects developed a post treatment abnormal result.

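### The SAP leaves out the protocol's any-post-baseline laboratory count and its post-treatment abnormal-ECG count, and its one-value-per-window rule can keep some abnormal results out of every summary table

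*SAP*

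**What the plan says.** **Protocol.** Section 8.9.2 commits to a subject-level laboratory summary: "Subjects with clinical laboratory values outside of the normal reference range at any post-baseline assessment will be summarized". Shift tables are promised in addition. Section 8.9.4 promises the overall ECG assessment "along with a summary of how many subjects developed a post treatment abnormal result". Sections 6.2.3 and 6.2.4 allow unscheduled labs and ECGs when clinically indicated. Section 5.6 refers to thyroid tests that are abnormal on two successive occasions, so repeat testing is foreseen.

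**SAP.** Section 2.4 ties summary tables to the scheduled time points. Within a window, "If more than one assessment is available within the range, the assessment closest to the target day is reported for the analyses window", and a tie goes to the earlier observation. Table 3 sets the Week 4 window at "Day 22 to Day 35" with target Day 29. The Week 10 window is everything after Day 57, with target Day 71 and no upper limit. Separately, "The Follow-Up assessment will be the last assessment available that is at least seven days after the end of treatment".

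Section 3.5.2 gives laboratory means and changes by analysis window, and "Shifts from baseline clinical laboratory values based upon the normal range will be tabulated for each post baseline sample timepoint". Section 3.5.4 gives the normal/abnormal ECG assessment by window. It adds "A summary of the number of subjects with a value > 450, 480 and 500" and counts of changes above 30 and 60, again by window.

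**The concern.** Taking the value nearest the target day suits means and changes over time. It does not suit counts of abnormal results, whose purpose is to show peaks whenever they occur. An abnormal result is a natural candidate for a retest. If the retest is normal and lies nearer the target day, or is the last value at Follow-Up, the tables show only the normal value.

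The protocol's two counts would have caught such results. Without them, rows by window cannot be added up to a number of subjects, because one subject may appear in several rows and a value that was not selected appears in none. Changes in laboratory and ECG parameters are named safety endpoints in both documents. What is at stake is whether the exceedance tables count every subject who had an exceedance.

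**Working it through.** The plan states no figure to reproduce. The check compares the two documents and then applies the SAP 2.4 selection rule to the visit days that the protocol allows.

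**1. Promised against planned**

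| Item | Protocol | SAP |
|---|---|---|
| Labs out of range, any post-baseline assessment | 8.9.2: yes | 3.5.2: absent |
| Lab shifts from baseline | 8.9.2: yes | 3.5.2: by timepoint |
| Subjects developing a post-treatment abnormal ECG | 8.9.4: yes | 3.5.4: absent; status by window only |
| QTcF threshold counts | not mentioned | 3.5.4: added, by window |

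SAP 3.5.2 and 3.5.4 specify no listing of post-baseline results either.

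**2. Visit days** (Baseline is Day 1; protocol 6.5)
- Week 4: 28 ± 3 days after Baseline, so Days 26 to 32.
- Week 10: 70 + 3 days, so Days 71 to 74.
- Follow-up for completers: 35 + 7 days after Week 10, so Day 71 + 35 = 106 to Day 74 + 42 = 116.
- ECGs are scheduled at Screening, Week 4 and Follow-up only (protocol Table 2). Post-baseline hematology and chemistry are scheduled at Week 4, Week 10 and Follow-up; endocrine labs at Week 10 and Follow-up.

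**3. Rule.** A retest displaces the original if it falls in the same window and |retest day − target| < |original day − target|.

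**(a) Week 4 visit then retest, labs and ECG, target Day 29**
- Day 26: distance 3, displaced by a retest on Days 27 to 31.
- Day 27: distance 2, displaced on Days 28 to 30.
- Day 28: distance 1, displaced on Day 29.
- Days 29 to 32: never displaced by a later retest.

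If every retest lag of 1 to 14 days is listed (an assumed range), displacement occurs in 5 + 3 + 1 = 9 of 7 × 14 = 98 combinations. This shows how narrow the route is; it is not a probability. The same listing for Week 10 visits on Days 71 to 74 gives 0 of 4 × 14 = 56, because every later day lies farther from Day 71.

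**(b) Unscheduled abnormal result with a nearer value in the window**
- QTcF above 500 on Day 33: distance 4 against 0 for a Day 29 ECG, so it is not counted.
- Abnormal lab on Days 58 to 67: distance 13 down to 4, against at most 3 for an on-schedule Week 10 lab, so it always loses.
- Abnormal lab on Days 68 to 70: loses only if the Week 10 visit is strictly nearer Day 71.

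**(c) Follow-up lab then retest.** The last value is used, so any later retest replaces the original in the Follow-Up row. The original cannot return through the Week 10 window when a Week 10 lab exists: its distance is at least 106 − 71 = 35, against at most 3.

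**(d) Follow-up ECG then retest.** Take an original on Day 106 and a retest on Day 113. The retest fills the Follow-Up row. No Week 10 ECG is scheduled, so the original, at distance 35 against 113 − 71 = 42, is reported in the open-ended Week 10 window. It is lost only if another ECG after Day 57 lies nearer Day 71. In an early stopper the retest itself can be that ECG. With a last dose on Day 30 and Follow-up on Day 65 (distance 6), a retest on Days 66 to 76 (distance 5 or less) takes both rows.

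**4. With any-post-baseline counts restored,** selection within a window no longer matters, and none of the cases above leaves a subject uncounted.

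**The case against.** The strongest reply is that the safety net has other strands and the gap is small. Most of that stands.

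- **Adverse events.** Protocol 7.1.3 has clinically significant laboratory and ECG abnormalities after first dose recorded as adverse events, and SAP 3.5.1 tabulates those. A reader might infer that displaced results vanish from all safety tables. The documents do not support that; the gap concerns results the investigator did not judge clinically significant. An objective threshold count should still not depend on that judgement.
- **Narrow on-treatment route.** A retest after an on-schedule Week 10 visit displaces nothing, and Week 4 is exposed only for visits on Days 26 to 28. No lab or ECG visit is scheduled at Week 2 or Week 6, so a lone unscheduled result in those windows is reported.
- **Follow-up ECGs.** A reader might infer that every Follow-up retest hides the original. That is true of labs when a Week 10 lab exists. For a completer's ECG it is normally false, as case (d) shows.
- **Direction of bias.** A reader might infer greater understatement in the arm with more abnormalities. That would require retesting to differ between arms, and no retest rate is given. The last-value rule can also replace a normal Follow-up result with a later abnormal one.
- **Shift-table wording.** The phrase about each sample timepoint in SAP 3.5.2 could mean every sample. SAP 2.4, and SAP 2.9 with its by-timepoint summaries, make scheduled time points the more natural reading. Even the generous reading yields no count of subjects out of range at any time.
- **What the protocol requires.** It promises neither QTcF threshold counts nor worst-value shifts, so their absence in any-time form is not a departure from it.

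None of this restores the two omitted summaries.

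**Conclusion.** The point holds as an omission from protocol to SAP with a limited but real consequence. Two promised subject counts are absent from the SAP sections where they belong. Followed as written, the SAP can leave abnormal results not recorded as adverse events out of every summary table, through routes (a) to (d).

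The size cannot be put in subjects: it depends on how often results are retested or taken unscheduled, which the documents do not give. The conclusion assumes that the window rule governs the shift and threshold tables, and that the Week 10 window is open-ended as Table 3 shows. The missing any-time counts do not depend on either assumption. The point concerns completeness of safety reporting; it is no evidence of a between-arm bias or of a hidden safety signal.

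**What to change.** Keep the SAP 2.4 window rule for means and change from baseline. Add to SAP 3.5.2 and 3.5.4, by treatment and from all scheduled and unscheduled post-baseline records:

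1. the number of subjects with any out-of-range value for each laboratory parameter (restores protocol 8.9.2);
2. the number of subjects who developed any post-treatment abnormal ECG (restores protocol 8.9.4);
3. the number of subjects with any QTcF above 450, 480 or 500, and with any change above 30 or 60. This extends the SAP's own thresholds and is not protocol text.

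State that these counts bypass the window selection. Shift tables to the worst value are optional; 8.9.2 does not call for them. The cost is a short SAP edit and a few extra table rows from data already collected, with no effect on trial conduct.
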